2	20-Jul-2019	To clarify ANCOVA analysis for Haemo-QOL for small sample size	Clarify that only the descriptive statistics will be provided if ANCOVA model does not converge due to small sample size in Section 6.3.3.4.
2	20-Jul-2019		An exploratory analysis to evaluate the association between the change in Haem-A-QOL physical health and total scores and ABR and concomitant pain medication use is added in Section 6.3.2.4.

SAP version number	Date approved	Rationale	Description of statistical changes
2	20-Jul-2019		An exploratory analysis of bleeding symptoms is added in Section 6.3.1.3.
2	20-Jul-2019	To be aligned with protocol amendment 02	'Adverse events of clinical interest (AECI)' is changed to 'Adverse events of special interest (AESI)' throughout. Systemic injection associated reactions (IARs) is added to the criteria of AESI in Section 6.6.2.
2	20-Jul-2019	To be aligned with Sanofi's standard analysis for Lab and vital sign.	Lab analysis by NCI CTCAE grade and shift tables are removed in Section 6.6.3 since PCSA analysis will be performed. Vital sign by PCSA is added in Section 6.6.4.
2	20-Jul-2019	To align the analysis reference date with Day 1 visit date when baseline assessments are done, fitusiran first dose is given, and eDiary is distributed to the patients.	The reference date is changed from randomization to Day 1 visit date in Section 5.2. The baseline definition is changed from randomization to Day 1 visit in Section 5.5.
2	20-Jul-2019	To define geographic regions	Geographic regions are defined in Section 5.11.
2	20-Jul-2019	AT lowering capacity of fitusiran is expected to achieve therapeutic target range at the end of the onset period for the 80 mg fixed dose. ABR by AT lowering analysis does not add much value to the ABR comparison between onset period and efficacy period.	The analysis of ABR by AT lowering in Section 6.4.3 is removed.

SAP version number	Date approved	Rationale	Description of statistical changes
2	20-Jul-2019	In addition to the primary analysis of ABR for the recurrence of events, it is also of interest to compare the time to first bleeding event between on-demand treatment and fitusiran prophylaxis treatment.	The exploratory analysis of time to first bleeding event is added in Section 6.3.1.3
2	20-Jul-2019	To include untreated bleed in the bleeding episode definition	The untreated bleed is included in the bleeding episode definition in Section 6.3.

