5 GENERAL STATISTICAL METHODS

5.1 Sample Size Justification

Assuming a mean ABR of 18 with standard deviation (SD) = 14 in the on-demand arm (patients randomized to receive on-demand bypassing agents) and a mean ABR of no more than 4 with SD = 6 in the fitusiran treatment arm (patients randomized to receive fitusiran) in either the efficacy period or treatment period, with a sample size of 14 evaluable patients in on-demand arm and approximately 28 evaluable patients in the fitusiran treatment arm, it is projected that the study will have greater than 90% power for testing treatment difference in mean ABRs. This power estimation was based on negative binomial regression model with a 2-sided type I error rate of 0.05.

The planned sample size is 54 randomized patients assuming a 20% drop-out rate.

In the China Addendum #1 to protocol amendment 2, it specifies that before any Chinese patients are randomized to receive 80 mg of fitusiran subcutaneous (SC) treatment, three (3) subjects in China will be enrolled into a China specific non-randomized fitusiran treatment arm to receive fitusiran as a SC injection administered every 4 weeks, with initial starting dose of 50 mg SC. After the observation period for these 3 patients is completed and dose escalation is authorized by the Sponsor, the 3 patients will undergo dose escalation to receive 80 mg of fitusiran as a SC injection every 4 weeks. These 3 patients will not be included in the ITT Set for the efficacy analyses but will be included in the Safety Set for the safety analyses. Their efficacy data will be included in separate listings.

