To evaluate the association between the change in Haem-A-QoL and other clinical measures, the analysis of change from baseline in the Haem-A-QOL physical health score and total score will be stratified by ABR level (0, >0 to <=5, >5) and concomitant pain medication use (Y, N). The ABR level is based on on-treatment strategy during the efficacy period.

The summary of adherence with Haem-A-QOL measurement will also be provided.

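### The Haem-A-QoL association analysis, on its natural reading, compares arms within post-randomisation ABR levels and plans no estimate of the association; two of the three levels should hold almost no on-demand patients

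*SAP*

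**What the plan says.** SAP 6.3.2.4 gives purpose and object in one sentence: "To evaluate the association between the change in Haem-A-QoL and other clinical measures, the analysis of change from baseline" in the physical health and total scores "will be stratified by ABR level (0, >0 to <=5, >5) and concomitant pain medication use (Y, N". The next sentence says that ABR level means on-treatment ABR in the efficacy period. SAP 2.6 records the same addition as "An exploratory analysis to evaluate the association between the change in Haem-A-QOL physical health and total scores and ABR" and pain medication use.

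The main analysis of change, earlier in SAP 6.3.2.4, is an ANCOVA with treatment arm, randomisation stratum and baseline scores. It reports least-squares means by arm and their difference, with a 95% CI and p-value. No coefficient for ABR or pain medication, no correlation and no comparison across ABR levels is specified. The association analysis is not in the hierarchy of SAP 5.7.

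**The concern.** The question is whether patients who bleed less report a larger improvement. An arm comparison inside an ABR level asks whether the arms differ among patients who bled about equally, which is a different null hypothesis.

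If fitusiran improves quality of life only by preventing bleeds, holding ABR roughly fixed removes most of the arm difference, so the within-level tests look null although the association is strong. If it acts by another route, those tests can be significant although ABR is unrelated to the score. ABR is also an outcome of treatment, so arms compared within an ABR level are no longer randomised groups.

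At stake is the interpretation of an exploratory result: a reader could take within-level arm tests as evidence for or against a link between bleeding and quality of life.

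**Working it through.** **Inputs.** SAP 5.1: "Assuming a mean ABR of 18 with standard deviation (SD) = 14 in the on-demand arm"; "a mean ABR of no more than 4 with SD = 6 in the fitusiran treatment arm"; "with a sample size of 14 evaluable patients in on-demand arm and approximately 28 evaluable patients in the fitusiran treatment arm". The efficacy period (SAP 6.3) is Day 29 to Day 246: 218 days, or T = 218/365.25 = 0.597 year.

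**Counts.** Mean μ = ABR × T; dispersion k = [(SD × T)² − μ]/μ².
- On-demand: μ = 10.74, k = 0.512.
- Fitusiran: μ = 2.39, k = 1.831.

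**The plan's own figure.** SAP 5.1 claims "greater than 90% power for testing treatment difference in mean ABRs", using a "negative binomial regression model with a 2-sided type I error rate of 0.05". A Wald test of the log rate ratio gives:
- SE² = (1/10.74 + 0.512)/14 + (1/2.39 + 1.831)/28 = 0.0432 + 0.0804 = 0.1236, so SE = 0.352.
- z = ln(18/4)/0.352 = 4.28, and power = Φ(4.28 − 1.96) = 99.0%.

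A simulated regression with common dispersion gives 98.7%. Using the fitusiran dispersion in both arms, the most conservative variant tried, gives 89.7%. The stated power is supported, so these inputs are a fair basis for expected stratum counts. The SAP gives no such counts itself.

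**Patients per ABR level.** One bleed in 218 days is an ABR of 1.68, two are 3.35 and three are 5.03. The levels therefore mean 0, 1–2, and 3 or more bleeds.

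| ABR level | On-demand share | of 14 | of 18 | Fitusiran share | of 28 |
|---|---|---|---|---|---|
| 0 | 2.6% | 0.4 | 0.5 | 39.9% | 11.2 |
| >0 to ≤5 | 9.6% | 1.3 | 1.7 | 28.9% | 8.1 |
| >5 | 87.8% | 12.3 | 15.8 | 31.2% | 8.7 |

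Applying the SDs to a one-year or treatment-period count instead gives 0.2 to 0.4 and 1.3 to 2.1 of 14 in the two lower levels.

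With 14 on-demand patients:
- ABR 0: none with probability 0.974^14 = 69%; at most one, 95%. At least two per arm occurs in about 5% of trials.
- >0 to ≤5: none, 24%; at most two, 86%. At least two per arm occurs in about 40% of trials.

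The SAP's minimum for fitting a bleeding model in a subgroup (6.3.1.4) is three patients per arm. It is not extended to this analysis. At >0 to ≤5 the on-demand arm would meet it in only about 14% of trials (100% − 86%).

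If ABR level is crossed with pain medication, about 0.4 + 1.3 = 1.7 on-demand patients are spread over four of the six cells. The pain medication split is not given.

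**Does the within-level arm test track the association?** This is an illustration; its quality-of-life effects are assumed, not taken from the documents. It uses 14 and 28 patients, 3,000 trials per row and a two-sample test within each level. Scenario A: the score changes 1 point per ABR unit, with no direct arm effect. Scenario B: a direct arm effect of 14 points (1 × (18 − 4), the same total effect) and no relation to ABR. Entries are rejection rates at two-sided 0.05.

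| Residual SD | A: arm test at ABR >5 | A: ABR slope | B: arm test at ABR >5 | B: ABR slope |
|---|---|---|---|---|
| 10 | 25% | 99% | 83% | 5% |
| 15 | 18% | 93% | 51% | 5% |
| 20 | 14% | 76% | 31% | 5% |

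A second set-up used ANCOVA within levels, sample sizes of 36/18 and 28/14, and effects in residual-SD units:
- Slope of 0.5 SD per unit of log(1+ABR), no direct effect: at least one within-level arm test was significant in about 10–12% of trials, against 79–91% for the ABR term in one regression.
- Direct effect of 1 SD, no association: 53–71% against about 5%.

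The sizes depend on the assumptions. The mismatch follows from testing a different null.

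**The case against.** The strongest objection is that the arm-comparison reading is inferred. The sentence names no model and no within-level p-value, whereas elsewhere in SAP 6.3.2.4 a rerun is stated outright as the same ANCOVA model. Stratified could mean ABR level as a model factor, or a summary by level, and either could show the association. This stands as a limit on certainty. It does not remove the gap, because no estimate of the association is specified under any reading.

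Second, by-level least-squares means could be read across levels within an arm, and the fitusiran arm fills all three (about 11, 8 and 9 of 28). In the second set-up at slope 0.5, the fitusiran mean at ABR >5 was worse than at ABR 0 in about 99% of trials, against about 50% with no association. So a reader who infers that the planned output must hide or reverse the association goes too far. That look would be informal, though, with no planned estimate or interval.

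Third, a reader might infer that most strata lack controls. The counts support two of three ABR levels, or four of six crossed cells. If the two factors are used separately, only two of five strata are shown to be sparse.

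Fourth, the simulated rejection rates compare tests of two different hypotheses under assumed effects. Counting any significant level as evidence of association is not an SAP rule. They illustrate the mismatch and do not predict this trial's result.

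**Conclusion.** The concern holds as a minor point. On its natural reading, the scheme estimates an arm difference at similar ABR and contains no planned estimate of the association it is meant to evaluate. In the two lower ABR levels, with about 0.4 and 1.3 of 14 expected on-demand patients, the arm comparison would mostly have no control patient or rest on one or two.

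The counts rest on the SAP 5.1 means and SDs, a negative binomial distribution and full 218-day follow-up. Actual numbers in the low levels are more likely to be lower: entry requires at least six treated bleeds in six months, Haem-A-QoL is limited to patients aged 17 or over, and it is not collected at early termination (Protocol Table 1, footnote s).

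A reader might infer that the Haem-A-QoL efficacy claim is compromised. The documents do not support that: SAP 2.6 labels this analysis exploratory and SAP 5.7 does not include it. The primary result, the main Haem-A-QoL comparison and type I error control are unaffected.

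**What to change.** Replace the stratification sentence in SAP 6.3.2.4 with the following, for each of the two scores:

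- Fit one exploratory model on all patients with data: change from baseline on baseline score, randomisation stratum, treatment arm and on-treatment ABR, entered as log(1+ABR) or as the three ordered levels. Report the ABR coefficient with its 95% CI.
- Fit a separate model with pain medication use (Y/N) in place of ABR, and report that coefficient with its 95% CI.
- A model with both may be added, noting that pain medication may lie on the path from bleeding to quality of life, so it can absorb part of the ABR association.
- Show results by ABR level descriptively (n, mean, SD, by arm), with no within-level arm test.
- Label all of this exploratory and observational.

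The cost is a short SAP edit and two small models per score, on data already collected. There are two downsides. The coefficients are observational, as any by-ABR comparison would be. Power is modest if the association is weak: in the second set-up, detection of the ABR term falls from 79–91% at a slope of 0.5 SD to about 42–52% at 0.3 SD.

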6.3.2.5 ABR in the onset period

Analysis will include all bleeding episodes between Day 1 visit and Day 28 (inclusive). The primary efficacy analysis will be repeated with this endpoint. No formal hypothesis testing will be performed; p-value will be deemed exploratory.

6.3.3 Exploratory Endpoints

6.3.3.1 TSQM-9

The Treatment Satisfaction Questionnaire for Medication (TSQM) version 9 assesses patient satisfaction with treatment. The TSQM Scale scores and their changes from baseline will be summarized.

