- q All patients will be tested for antibodies to fitusiran at the Screening visit. After randomization, testing for antibodies to fitusiran will be performed in the fitusiran treatment arm only.
- r Blood samples for PK analysis will be collected at the time points listed in Table 7 in all fitusiran arm patients. In East Asian patients in the fitusiran arm at East Asian sites, blood samples for PK analysis will be collected at the time points listed in Table 8 (which includes all those time points listed in Table 7), and pooled urine samples will be collected for PK analysis at the time points listed in Table 9.
- s Must be completed at the clinic. Will be collected at EOS visit; not collected at ET visit.
- t Will include review of entries, (symptoms of bleed events, bleed causality, bleed severity, doses administered), whether appropriate site contact occurred regarding treatment of bleeds, and review of patient bleed management plan and recommendations and requirements for site contact regarding dosing.
- u It is strongly preferred that BPA administration and bleeding events are entered in the eDiary immediately or within 24 hours. Additional patient follow-up may be required as described in Section 7.2.1. Patients in the fitusiran treatment arm who present in the clinic with symptoms characteristic of a potential bleeding episode should have assessments completed per Table 2.
- v Perioperative assessment safety and hemostatic efficacy only in patients undergoing operative procedures while on study (see Table 10).
- w AEs will be monitored and recorded from date of signed informed consent through Follow-Up. Signs and symptoms of thrombosis will be evaluated at every visit (see Section 6.5)
- x In addition to recording concomitant medications, documented history of prior medications will be collected during Screening.

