3.1.3 Exploratory Objectives

- To evaluate the effects of fitusiran as compared to on-demand treatment with bypassing agents on the following patient reported outcomes:
 - Patient satisfaction with treatment
 - Patient activity
 - HRQOL in adolescents (≥ 12 to < 17 years of age)
- To determine the pharmacodynamic (PD) effect, pharmacokinetics (PK), and immunogenicity of fitusiran
- To evaluate the effects of fitusiran as compared to on-demand treatment with bypassing agents on the total weight-adjusted consumption of bypassing agents
- To evaluate the effects of fitusiran as compared to on-demand treatment with bypassing agents on joint status
- To evaluate the effects of fitusiran as compared to on-demand treatment with bypassing agents on patient resource use

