3.2 Endpoints

3.2.1 Efficacy Endpoints

Primary and secondary endpoints for Global and US protocols are in the table below.

	Global Protocol	US Protocol
Primary	Annualized Bleeding Rate (ABR) in the efficacy period	ABR in the treatment period
Secondary	ABR in the treatment period	ABR in the efficacy period
	Annualized spontaneous bleeding rate in the efficacy period	
	Annualized joint bleeding rate in the efficacy period	
	Change in Haem-A-QOL physical health score and total score in the treatment period	
	ABR in the onset period	

Exploratory Efficacy Endpoints

- Change in the following in the treatment period:
 - Treatment Satisfaction Questionnaire for Medication (TSQM) domain scores
 - Haemophilia Activities List (HAL) score
 - Paediatric HAL (pedHAL) score
 - EuroQOL-5 dimension (EQ-5D) score
 - Haemo-QOL score
 - Hemophilia Joint Health Score (HJHS)
- Number of target joint bleeding episodes
- Annualized weight-adjusted consumption of bypassing agents
- Change in patient resource use (eg, work/school attendance, visits to doctor/hospital)

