5.5 Baseline Definitions

Unless noted otherwise, baseline for on demand group is defined as the last non-missing value on or before Day 1 visit. Baseline for fitusiran group is defined as the last non-missing value before 1st dose of fitusiran or the last non-missing value on or before randomization date for patients who were randomized but never exposed to fitusiran.

ECG measurements are taken in triplicate. For the on demand group, the average of the first triplicate readings on or before Day 1 visit or on screening visit will be used as baseline. For fitusiran group, the average of the last triplicate readings before 1st dose is used as baseline.

For questionnaire assessments, the last non-missing value on or before Day 1 visit will be used as baseline. For fitusiran patients, the last non-missing value on or before date of 1st dose of fitusiran or the last non-missing value on or before randomization date for patients who were randomized but never exposed to fitusiran will be used as baseline.

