6.3.3.2 HAL and pedHAL

The Haemophilia Activities List (HAL, in patients ≥ 18 years of age) and pediatric HAL (pedHAL, in patients < 18 years of age) questionnaires assess subjective functional ability to perform activities of daily living. Overall score, component scores, domain scores, and their changes will be summarized by scheduled visits.

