6.3.3.3 EQ-5D-5L

The EQ-5D-5L is a standardized instrument for use as a measure of QOL outcome. Index value and visual analogue scale (VAS) score and their changes from baseline will be summarized. Numbers and percentages of patient by level and dichotomized level (1 = no problems, 2 to 5 = “problems”) of each dimension will be reported.

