6.3.3.4 Haemo-QOL

The Haemo-QOL will be provided to patients < 17 years of age. The change from baseline in total score of Haemo-QOL will be analyzed using an analysis of covariance (ANCOVA) model with fixed effects of treatment arm and randomization strata of the number of bleeding episodes in the 6 months prior to study entry (≤ 10 vs > 10), baseline Haemo-QOL total score as covariate. Domain scores for Haemo-QOL and their changes from baseline will be summarized descriptively. Only the descriptive statistics will be provided if ANCOVA model does not converge due to the small sample size.

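### TSQM-9 and HAL serve a comparative exploratory objective, but the SAP specifies no arm difference, confidence interval or baseline adjustment for them

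*SAP*

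**What the plan says.** SAP 3.1.3 words the objective as a comparison: "To evaluate the effects of fitusiran as compared to on-demand treatment with bypassing agents on the following patient reported outcomes". It then lists satisfaction, activity and adolescent HRQOL. The matching endpoints in SAP 3.2.1 are changes over the treatment period, the first being "Treatment Satisfaction Questionnaire for Medication (TSQM) domain scores".

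The analysis text is shorter. For TSQM-9, SAP 6.3.3.1 has "The TSQM Scale scores and their changes from baseline will be summarized". For HAL and pedHAL, SAP 6.3.3.2 has "Overall score, component scores, domain scores, and their changes will be summarized by scheduled visits". For EQ-5D-5L, SAP 6.3.3.3 has "Index value and visual analogue scale (VAS) score and their changes from baseline will be summarized", plus counts by response level. None of the three sections names a model, an arm difference or an interval, and none says that the summaries are by arm. Protocol 8.2.5.3 leaves exploratory analyses to the SAP, so no other text fills this in.

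The data for an adjusted comparison are planned. Protocol Table 1 schedules the questionnaires on Day 1 and at the end-of-study (EOS) visit, and SAP 5.5 states: "For questionnaire assessments, the last non-missing value on or before Day 1 visit will be used as baseline", with a matching rule tied to the first dose for fitusiran patients. One exploratory questionnaire does get a model. SAP 6.3.3.4 says: "The change from baseline in total score of Haemo-QOL will be analyzed using an analysis of covariance (ANCOVA) model", with arm, stratum and baseline score as terms. If that model does not converge because of small numbers, only descriptive statistics are given.

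**The concern.** The objective asks how the arms compare, and the planned output describes scores and changes. A reader of the study report would probably set two mean changes side by side, without an interval and without allowance for different starting points. In a trial of this size, arms can differ at baseline by chance on scores that are not stratification factors. A patient group that starts worse tends to improve more, whatever the treatment.

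The choice of where to model also looks uneven. The adjusted model is planned for the smallest questionnaire group, patients under 17, and not for TSQM-9 or HAL, which are given to most of the trial.

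The stake is limited to the precision and readability of two exploratory comparisons. The primary analysis, the sample size and the testing hierarchy are not affected.

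**Working it through.** **Inputs from the documents.** The plan is for 54 randomised patients at 2:1 (36 + 18), 20% drop-out, and 28 + 14 evaluable patients (SAP 2.2 and 5.1; Protocol 1.3). About 5 adolescents aged 12 to under 18 are planned (Protocol 4.3). HAL is for patients aged 18 or over and Haemo-QOL for those under 17 (SAP 6.3.3.2 and 6.3.3.4). The questionnaires carry a footnote in Protocol Table 1: "Will be collected at EOS visit; not collected at ET visit".

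**Assumed.** The documents give no SD or correlation for these scores. I take equal baseline and follow-up variances and a correlation r of 0.3, 0.5 or 0.7.

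**The plan's own numbers.** 42 / 0.8 = 52.5, so 53 patients, against 54 planned; 54 fits the 2:1 ratio as 36 + 18. The stated power concerns ABR only, so there is no power figure for TSQM-9 or HAL to reproduce.

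**Precision.** In units of the score variance, raw change has variance 2(1 − r) and the ANCOVA residual has 1 − r². The SE ratio is √[(1 − r²) / (2(1 − r))] = √[(1 + r)/2]:
- r = 0.3: √0.65 = 0.81
- r = 0.5: √0.75 = 0.87
- r = 0.7: √0.85 = 0.92

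**95% CI half-widths, in score SDs.** For ANCOVA the half-width is t × √(1 − r²) × √(1/n₁ + 1/n₀), with df = n − 4 (intercept, arm, stratum, baseline). For raw change it is t × √(2(1 − r)) × √(1/n₁ + 1/n₀), with df = n − 2. Small inflation from covariate imbalance is ignored. For HAL, 54 − 5 = 49 adults, and 49 × 0.8 ≈ 39, taken as 26 + 13.

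| Score | ANCOVA df | Method | r = 0.3 | r = 0.5 | r = 0.7 |
|---|---|---|---|---|---|
| TSQM-9 (28 + 14) | 38 | ANCOVA | 0.63 | 0.57 | 0.47 |
| | | Raw change | 0.78 | 0.66 | 0.51 |
| HAL (26 + 13) | 35 | ANCOVA | 0.66 | 0.60 | 0.49 |
| | | Raw change | 0.81 | 0.69 | 0.53 |

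**Chance imbalance.** The SD of the baseline mean difference is √(1/28 + 1/14) = 0.33 score SDs. Given an imbalance of that size, the raw change difference is shifted by 0.33 × (1 − r), which is 0.23, 0.16 or 0.10 SDs. This shift is one component of the wider raw-change intervals above, not an extra cost.

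**The Haemo-QOL model for contrast.** Haemo-QOL stops at age 17, so 5 patients is an upper planning figure. With 5 patients, df = 5 − 4 = 1 and t = 12.7. For a 3 + 2 split, √(1/3 + 1/2) = 0.91, and the half-width is 11.1, 10.1 or 8.3 SDs at the three correlations. With 4 patients there are 0 df, so no interval exists. Least-squares ANCOVA has a closed-form solution, so a non-convergence rule would not reliably prevent a 1-df fit.

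**The case against.** The other side has a good case. These endpoints are exploratory and outside the hierarchy in SAP 5.7, the protocol defers to the SAP, and descriptive reporting of patient-reported outcomes in an open-label trial is defensible. That stands: this is an improvement to the plan, not a conflict or an error in it. Descriptive-only is not, however, this SAP's general rule for exploratory work. It plans a Cox model for time to first bleed (6.3.1.3) and ANCOVA for Haemo-QOL (6.3.3.4). In 6.3.2.5 it also shows how to present a modelled comparison whose p-value is only exploratory.

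Several stronger readings are tempting and are not supported.

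- A reader might infer that the comparative question cannot be answered at all. SAP 5.2 provides n, mean and SD for continuous variables. If these are tabulated by arm, they give an unadjusted difference in change and its interval.
- A reader might infer that raw change is biased. Under randomisation it is unbiased on average; chance imbalance costs precision.
- A reader might count EQ-5D among the comparative objectives. It has no objective of its own, and HRQOL from age 17 already gets an adjusted arm difference through Haem-A-QoL (SAP 6.3.2.4).
- A reader might say that the sponsor overlooked the small Haemo-QOL group. The descriptive fallback shows that small numbers were anticipated, although its trigger is weak.
- A reader might compute imbalance from 36 v 18, which gives √(1/36 + 1/18) = 0.29. That is everyone randomised. With EOS-only collection and 20% drop-out, about 28 v 14 is closer to the analysed set.

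Two further limits stand. TSQM and HAL are given only where a version is available (Protocol 7.6.1.2 and 7.6.1.3), so numbers may be lower. HJHS and resource use also have comparative objectives and are only summarised; this point does not extend to them.

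**Conclusion.** The point holds for TSQM-9 and HAL as a low-priority improvement. The SAP states a comparison on satisfaction and activity but specifies no arm difference, interval or baseline adjustment, although baseline scores are collected and defined. What is lost is precision and a stated estimate, not the ability to compare. At 28 v 14 evaluable patients, adjustment would narrow the TSQM-9 interval half-width from 0.78, 0.66 or 0.51 to 0.63, 0.57 or 0.47 score SDs. These sizes rest on the assumed correlations of 0.3 to 0.7 and on equal variances, neither of which is in the documents. The gain shrinks as the correlation rises.

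The Haemo-QOL model shows that the sponsor already accepts this form of analysis for an exploratory questionnaire, in a group where it leaves about 1 residual df.

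**What to change.** Add one sentence each to SAP 6.3.3.1 and 6.3.3.2. For the TSQM domain scores and the HAL overall score, report the difference between arms in change from baseline, with its 95% CI, from an ANCOVA with arm, randomisation stratum and the baseline value of the same score. State that the result is exploratory and outside the testing hierarchy, and that the descriptive tables are by arm. EQ-5D index and VAS may be added in the same form as an option; the ordinal dimension levels should stay as counts. Keep pedHAL descriptive, because very few patients will complete it.

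Note alongside the results that early withdrawals have no EOS questionnaire, so the model covers completers only. The planned summaries share this limit.

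The cost is SAP wording before database lock and a few more runs of a model already in the plan. No data collection, sample size or alpha changes.
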